3.6.3.3 Evaluation of inclusion and exclusion criteria

The subjects are presented in written form the exclusion and inclusion criteria in the recruitment phase (Appendix 1 - Recruitment notice) and in the information regarding the study (Appendix 2 - Participant information and consent form).

After the subject has signed up to the study and filled the first set of questionnaires (T0), the clinical subject coordinator (CSC) calls them via phone to confirm they meet the inclusion and do not meet the exclusion criteria (Appendix 5 - Clinical Subject Coordinator phone call). See section 3.6.5.2.

3.6.3.4 Discontinuation criteria

The coordinating investigator may discontinue the study for the subject if

- Subject has an adverse event (AE) related to the device use
- Subject violates the Appendix 3 (Confidentiality obligation and right of use)
- Subject’s mental health deteriorates in a way that they are not fit for continuing in the study. This includes, for instance, psychotic symptoms, hospitalisation, and suicidality.

If the subject has a serious adverse event (SAE) their participation in the study is discontinued. For more information on the protocol regarding adverse events and serious adverse events, see section 3.14.5.

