3.7.2 Data-analysis-inclusion criteria and handling of missing data

To be included in the analysis of the primary hypothesis, the subject has to

- Have played the game version A or B at least 24 hours (50% of the recommended 48 hour game time) during the 12 weeks.
- The subjects must have answered all of the PHQ-9 items on both T0 and T2 or T3.

Handling of missing data:

- Primary endpoint evaluation will be based on the comparison of scores acquired ~~at~~ between T0 and T3.
- When the subject has played the MEL-T01 or MEL-S01 for 24 hours, but the T3 PHQ-9 score is missing, we will use the T2 PHQ-9 score.
- If the subject has accumulated ≥ 24 hours of intervention use and then ceased the use, we will use the first PHQ-9 score after the cessation of use.
- Subjects that do not meet these criteria are excluded from the analysis.
- In regards to our secondary hypotheses, missing data are handled similarly.

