3.7.5 Interim analysis

Interim analysis in clinical trials is an analysis, and hence unblinding, of partially acquired data, which is conducted before the data collection has been completed. This can be performed to assess whether the investigational device can be proven to be (i) clearly beneficial or (ii) harmful compared to the comparator, or to be (iii) obviously futile.

We will use a pre-defined and pre-programmed interim analysis to assess these three conditions and thereafter infer whether the investigation should be stopped early or if the investigation plan warrants a change in terms of the to-be acquired cohort size. If evidence for one alternative is acquired, such modifications allow the saving of resources and subjects' efforts.

The interim analysis will be conducted when each arm has 33 or more subjects that have completed the 12 first weeks of the investigation and meet the inclusion criterion to data analysis (see [3.7.2](#)).

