Follow-up. The coordinating investigator will follow the AE, SAE, or device deficiency with examining its connection with the device use. When necessary, a patch process is undertaken as described in 3.14.2 The AE and device deficiency are reported to regulatory bodies, including FIMEA and HUS ethical board, according to regulatory schedules. SEA are reported without delay and within a maximum of 7 days to the relevant regulatory bodies as well as research sites.

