3.15.2 Temporary halt or early termination of an investigation

3.15.2.1 Halt or termination for one subject

As per 3.6.3.4, the coordinating investigator may discontinue the study for the subject if

- Subject has an adverse event (AE) related to the device use
- Subject violates the Appendix 3 (Confidentiality obligation and right of use)
- Subject's mental health deteriorates in a way that they are not fit for continuing in the study. This includes, for instance, psychotic symptoms, hospitalisation, and suicidality.

If the subject has serious adverse events (SAE) their participation in the study is discontinued. If the study needs to be terminated early for a subject, the subject is contacted through the phone, and the reasoning for discontinuation is discussed with them.

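### An SAE ends study participation in every arm and no later PHQ-9 is described, so the primary comparison drops these subjects or may score them on a pre-event T2 value; the effect is probably small

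*Combined protocol and SAP*

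**What the plan says.** Section 3.6.3.4 makes discontinuation after an SAE mandatory: "If the subject has a serious adverse event (SAE) their participation in the study is discontinued". By contrast, a device-related AE or a deterioration in mental health may end participation, at the coordinating investigator's discretion. Section 3.15.2.1 repeats both rules. Section 3.3.1.4 counts hospitalisation and threat to life among SAEs.

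Two procedures are described for a single discontinued subject. Section 3.15.2.1 says that "the subject is contacted through the phone, and the reasoning for discontinuation is discussed with them". Section 3.14.1 says: "The coordinating investigator will follow the AE, SAE, or device deficiency with examining its connection with the device use". Neither mentions a questionnaire. Section 3.6.3.4 also gives a pointer, "For more information on the protocol regarding adverse events and serious adverse events, see section 3.14.5", but no section with that number appears in the contents list or the text.

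Section 3.7.2 sets the primary analysis set. A subject must "Have played the game version A or B at least 24 hours" and have a complete PHQ-9 at T0 and at T2 or T3. If a subject has played 24 hours "but the T3 PHQ-9 score is missing, we will use the T2 PHQ-9 score". If use stopped after at least 24 hours, "we will use the first PHQ-9 score after the cessation of use". Everyone else is excluded.

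**The concern.** In a depression trial, admission for worsening depression is both an SAE and a poor result on the primary endpoint. A rule that ends participation at that point, with no later PHQ-9, removes outcome data because of the outcome. Section 3.7.2 then either drops the subject or may use a score from before the event. The post-cessation rule in 3.7.2 shows that the sponsor wants a score from after stopping, but the discontinuation rule leaves it without data. If SAEs were unbalanced between arms, the T0 to T3 comparison could not show it, and no sensitivity analysis is described that would.

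**Working it through.** **Inputs from the plan.** 133 per arm, d = 0.40, two-tailed alpha 0.0167 and power 0.80 (3.7.4.1); 24 h minimum play (3.7.2); 4 h per week recommended (3.1.6) and 2 h per week as the minimum pace (3.10.1); no SAEs among 54 pilot subjects (3.3.1.1).

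**Assumptions, because the plan gives no figures.** SD of PHQ-9 change is 5 points. SAE subjects end G = 5 to 10 points worse than their arm's mean. SAEs are spread evenly over 12 weeks. All other subjects reach 24 h. A T2 value from before the event equals the arm mean. The 24 h criterion is taken to apply to the device arms only, since TAU subjects have no device access before T3.

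1. *The plan's own figure.* An exact two-sample t-test has power 0.799 at 132 per arm and 0.803 at 133, so 133 is reproduced. Then 3 × 133 = 399, rounded to 400, and 400 / 0.50 = 800. This does not test the point, but it supplies the denominator.

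2. *Rule trace for a subject stopped by an SAE before T3.*
   - Device, under 24 h played: excluded by the 24 h rule in any case, so the SAE rule is not the cause.
   - Device, at least 24 h, stopped before T2: no T2 or T3 score, excluded.
   - Device, at least 24 h, stopped between T2 and T3: scored on T2.
   - TAU, stopped before T2: excluded.
   - TAU, stopped between T2 and T3: scored on T2 or excluded. The inclusion criterion accepts T2, but the substitution rule is worded only for players.

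   On no path does a described post-event PHQ-9 enter the comparison.

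3. *Shift per net excess subject.* Restoring one subject to an arm of 133 moves its mean by G/134: 5/134 = 0.037 and 10/134 = 0.075, about 0.04 to 0.07 points. The planned effect is 0.40 × 5 = 2.0 points.

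4. *Equal SAE rate r in all arms.* TAU loses r × G from its mean. A device arm also loses r × G, by different routes. At 4 h per week, 24 h is reached at week 6: 6/12 = 50% of its SAEs are lost to the 24 h rule, 2/12 = 17% are excluded for want of T2, and 4/12 = 33% are scored on T2. At 2 h per week, 24 h is reached only at week 12, so all are lost to the 24 h rule. The contrast shifts by rG − rG = 0. At r = 2% each arm mean moves by 0.02 × 5 = 0.10 to 0.02 × 10 = 0.20 points, and these cancel.

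5. *Departures from zero.* With a net excess of 2% (0.02 × 133 = 2.7 subjects) the contrast moves by 0.10 to 0.20 points. If rates are equal but half the worsening already shows at T2, and TAU subjects stopped after T2 are excluded rather than scored, the residual at 2% is 0.33 × 0.5 × 0.02 × G = 0.02 to 0.03 points.

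6. *Continuing questionnaires but keeping the 24 h rule, at equal rates.* All TAU subjects return, but only a fraction f of device subjects (f = 0.5 at 4 h per week, 0 at 2 h per week). The bias towards the device is rG − f r G/(1 − r + f r).
   - r = 2%: f = 0.5 gives 0.05 to 0.10; f = 0 gives 0.10 to 0.20.
   - r = 5.4%, the 95% upper bound for 0 of 54 (1 − 0.05^(1/54) = 0.054): f = 0.5 gives 0.13 to 0.26; f = 0 gives 0.27 to 0.54.

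**The case against.** The strongest reply is that nothing in the plan says questionnaires stop after an SAE. The referenced section is missing, and the appendices were not available for this review. Section 3.15.2.2 does provide for subject follow-up after a trial-wide halt, so termination and follow-up are not incompatible in this plan. This stands as a limit: the point is read from silence. Still, 3.15.2.2 does not apply to one discontinued subject, and the post-cessation rule selects a score without ordering one to be collected.

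Second, the effect may be negligible. Section 3.3.1.4 calls the risk of serious adverse effects very low, many SAEs need not involve worse depression, and the plan already assumes 50% dropout. This stands too and sets the priority. The assumed gap of 5 to 10 points for every SAE leans towards a larger effect.

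A reader might go further and infer that the rule tilts the result towards the device. The documents do not support that. They give no SAE rates by arm, the rule applies to every arm, MEL-T01 and MEL-S01 are treated alike, and equal rates give a shift of about zero.

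A reader might also infer that harm monitoring is lost, or that nobody stopped before week 12 can enter the interim harm test. Section 3.7.5 requires 33 subjects per arm who have "completed the 12 first weeks of the investigation and meet the inclusion criterion to data analysis", but that sets when the analysis runs, not who enters it. A device subject with 24 h and a T2 score meets 3.7.2. SAEs are recorded, reported and followed under 3.14.1 and can stop the trial under 3.15.2.2. What remains is that the interim harm test uses the same T0 to T3 PHQ-9 change and so shares the gap in scores.

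**Conclusion.** The point holds in limited form. As written, the plan ends participation after any SAE and describes no later PHQ-9. Subjects stopped before T2 leave the primary comparison; device subjects with at least 24 h who are stopped between T2 and T3 enter on a pre-event score; TAU subjects stopped in that interval have no clear rule. The loss is from the PHQ-9 comparison, not from the safety record.

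Against a planned effect of 2.0 points (SD 5 assumed), the between-arm effect is about zero at equal rates and gaps, and 0.04 to 0.07 points per net excess subject otherwise. Its sign is unknown. In the device arms the 24 h rule accounts for half or all of the loss, depending on pace of play. Confidence is medium, because the reading rests on silence and the rates, gaps and timing are assumed. This is a low-priority, inexpensive improvement.

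**What to change.** 1. In 3.6.3.4 and 3.15.2.1, let an AE, SAE or deterioration end device use only (for TAU, the later device period). Continue the T1 to T4 online questionnaires in every arm unless the subject declines, withdraws consent or is judged unable to take part. In 3.7.2, state that a score after cessation takes precedence over T2, and say whether T2 substitution applies to TAU. Correct the reference to 3.14.5.
2. Together with 1, add an analysis of the primary endpoint in all randomised subjects with a T0 and a later PHQ-9, regardless of the 24 h rule. Without it, step 1 returns more TAU than device subjects and favours the device.
3. Report by arm how many subjects have no PHQ-9 after the event, and why. Repeat the analysis in 2 with their change set 0, 5 and 10 points worse than their arm's mean.

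The cost is an ethics amendment (3.12.1) and some contact with unwell subjects, whose fitness to answer must be judged each time. The questionnaires are already emailed and completed online (3.10.1), and coordinator calls are already scheduled at weeks 4, 8, 12 and 24 (3.14.1). The target of 133 per arm is unchanged. Step 1 helps only subjects still in follow-up, and version 2.3 (26 February 2024) postdates the planned completion of 31.12.2023. Steps 2 and 3 can use data already collected.

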3.6.3.5 Subject monitoring

The subject answers to the clinical questionnaires are monitored. Particularly if the subject answers that they have suicidal ideation, they are given support text as indicated in Appendix

11 (Ethics evaluation of the study) and contacted by the clinical subject coordinator for support and guidance towards healthcare and other support resources.

3.6.3.6 Size of investigation population

Pirkola et al. (2005) found that prevalence of MDD in Finland is 4.9% in a representative adult sample ($N = 6005$).

According to Statistics Finland, there are 3 119 000 people between 20 and 64 years of age on 31.12.2020. This means that there are 153 000 20-64-year old people who suffer from MDD in Finland. This is the maximum size of the investigation population, considering that we focus on the Finnish population, and this maximum population is further reduced when other inclusion and exclusion criteria are applied.

We aim to reach the investigation population through contacts with HUS psychiatry and VSSHP psychiatry as well as through online recruitment using, for instance, Mielenterveystalo.fi webpages.

3.6.3.7 Representativeness of investigation population in relation to target population

Our target population are people who suffer from MDD. We believe that through our recruitment process, we are able to reach a relevant population sample. Through HUS and VSSHP psychiatry we are able to recruit subjects who have more severe MDD symptoms. Through online recruitment we are able to reach subjects who have lesser MDD symptom severity.

We also gather demographic information with background questionnaires through which we can analyse the representativeness of the sample gathered and compare it in demographic terms of age, gender and education to see how well it represents the population (see 3.7.1.1.).

3.6.4 Measures to minimise bias

3.6.4.1 Blinding

In order to ensure minimum bias, the main study is double-blinded so that neither the subjects nor the investigators, CSCs in particular, know whether any given subject is randomised to the MEL-T01 or MEL-S01 study arm. Investigators are aware of which subjects are randomised to the TAU arm but will be blinded to the subsequent intervention of the TAU-arm subjects with MEL-T01 or MEL-S01 after their initial follow-up period has ended.

3.6.4.2 Randomisation

The recruited MDD subjects are randomised into the MEL-T01, MEL-S01, and TAU arms in blocks of six consecutive subjects so that two subjects are allocated into each arm and so that one subject in the TAU arm will receive MEL-T01 and the other TAU subject MEL-S01 at the end of their initial 12-week follow period.

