The subjects ($N = 800$) volunteering to participate in this investigation are diagnosed with MDD and have an on-going mental health treatment contact with a mental health professional. The subjects are recruited through Helsinki and Uudenmaan sairaanhoitopiiri (HUS) psychiatry and Varsinais-Suomen sairaanhoitopiiri (VSSHP) psychiatry as well as online.

The subjects are randomised into three arms with equal probabilities in blocks of six consecutive subjects. Subjects in the MEL-T01 and MEL-S01 arms are engaged in the intervention for 12 weeks while those in the TAU arm are on a follow-up period during these 12 weeks.

After this 12-week period, the subjects in MEL-T01 and MEL-S01 arms enter a 12-week follow-up period and the subjects in TAU arm engage with either the MEL-T01 or MEL-S01 intervention (randomised at T0 with equal probability) for 12 weeks (See Table 1 below).

The subjects are recommended to play the investigational-device game for a total of 48 hours during the 12 weeks of active intervention with a recommended weekly dose of 4 hours. A minimum of 24 hours is needed for inclusion to hypothesis testing. The subjects are limited to a daily maximum of 1.5 hours of game time.

Prior to the intervention, a clinical interview (MINI) is performed via phone to confirm the subject's MDD diagnosis. The subjects' mental health symptoms and well-being are evaluated through online questionnaires five times: before subjects are randomised into one of the three groups (T0), and then 4 (T1), 8 (T2), 12 (T3), and 24 (T4) weeks after the study has begun.

Subject population:**Criteria for inclusion:**

Eligible subjects must fulfil all of the following criteria:

1. Between 18-65 year-old
2. Suffering from major depressive disorder
3. Have an ongoing mental health treatment contact to basic healthcare, specialised healthcare, student healthcare or occupational healthcare
4. Has sufficient eyesight with or without prescription
5. Has a Windows computer with internet connection and mouse
6. Has email and phone number

Criteria for exclusion:

Subjects who fulfil any of the following criteria are excluded from the study:

1. They have threat of self-harm
2. They have addiction to digital games
3. They have psychotic disorders
4. They are pregnant or breastfeeding
5. They have impaired ability in decision making
6. They are prisoner or forensic subject
7. They have neurological disorders such as epilepsy or brain injury

Safety assessments:

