3.6.4.3 Investigation data exempt from blinding

For the purpose of **subject monitoring**, the CSCs and excluding all other investigators, will have access to the gaming-time and questionnaire-completion-status data of individual identifiable subjects. This information will be available to the CSCs for AE report, email, or

phone call interactions with the subjects so that the CSCs are able to make informed inferences, e.g., about the subject's study compliance. Notably, the CSCs will also have access to the suicidality-related questionnaire responses for subject monitoring as specified in [3.6.3.5](#). The CSCs remain blinded to all other investigation data, and especially the data about the study arm, game performance, and all other questionnaire replies of the subjects.

For the purpose of **study monitoring**, the investigators, excluding the CSCs, will have access to the gaming-time, questionnaire-completion-status, and study-arm data of individual but unidentifiable subjects. These data will enable the assessment of whether the criteria for the interim analysis or study completion are met.

- These data are needed because the interim analysis (see [3.7.5](#)) is triggered when each arm has 33 subjects that have completed the intervention (specifically, the 12 first weeks, which are follow-up for the TAU arm) and meet the inclusion criterion (see [3.7.2](#)) to data analysis.
- Conversely, termination of the investigation (see [3.7.4.2](#)) will be triggered when each arm has 133 subjects that have completed both the intervention and the follow-up period and meet the inclusion criterion (see [3.7.2](#)) to data analysis.

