3.6.5.2 Clinical interview

A clinical interview is conducted after the subject has enrolled in the study but prior to the beginning of the intervention. The aim of the clinical interview is to evaluate the subject inclusion and exclusion criteria.

The subject's MDD diagnosis is evaluated using the MINI International Neuropsychiatric Interview Module A, Major Depressive Disorder (Sheehan et al., 1998). We use MINI version 6.0 that has been translated into Finnish. Only the patients who fulfil the criteria for MDD are included in the study.

We are aware that the inclusion criteria for study is MDD of which the symptoms by definition include suicidal thoughts. At the same time, the threat of self-harm is an exclusion criteria for the study. Should the patient indicate suicidal thoughts or deeds in the interview, they are pursued further in order to evaluate whether the subject meets the exclusion criteria for threat of self-harm.

If the subject has suicidal thoughts but the subject is aware of the thoughts and it is clear that they are not intending to act on them, the subject may be included in the study. If the suicidal thoughts are excessive, the subject is considerably hopeless, has explicit plans or intention of suicide, they are excluded from the study.

If the CSC is not certain whether to include the subject into the study or not, MINI Module B, Suicidality, is conducted. A score of 17 or more points is used as a definitive cut-off point, yet the CSC may use a lower score at their discretion.

The exclusion criteria “They have addiction to digital games” includes addiction to both entertainment games and gambling, and CSC asks the subject of both. If CSC is uncertain whether the subject suffers from gambling addiction, they conduct the Problem Gambling Severity Index (PGSI) as an interview holding 8 points as absolute exclusion criteria, however, they can use a lower cutoff point based on their evaluation. If CSC is uncertain about a subject's addiction to digital games, they conduct Game Addiction Scale (GAS) as an interview, holding four or more answers of “sometimes” or more frequently as absolute exclusion criteria, however, the CSC may hold a lower threshold if necessary.

When needed, the subjects are guided towards their healthcare providers and other health resources as needed.

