3.10.2 Research staff deviations and violations

The nature of clinical investigation is double-blinded. The information regarding the subject group is withheld from all researchers, including the CSC who are in direct interaction with the subjects as well as from the researcher conducting the experimental interview. Thus, we mitigate the risk of breaking the blind. The rest of the interactions between the subject and the researchers is avoided. If the subject contacts the researchers or coordinating investigator, the researchers are not aware of the subject group.

The CSC are trained in using MINI to ensure the inclusion and exclusion criteria are met. There are at least two CSC to ensure sufficient human resources to keep contact with the subjects.

The subjects are encouraged to report all AE and SAE to the researchers, and they have multiple channels to do so: in-game link, email, and phone calls.

After randomisation, the subjects are randomised to three groups. The groups are handled automatically to prevent mishandling samples.

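### A constant block of six printed in the plan, with contradictory text on who knows TAU status, makes some TAU-versus-game allocations foreseeable at screening; the 28.9% share is a ceiling, and random block sizes would cut it cheaply

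*Combined protocol and SAP*

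**What the plan says.** **Block rule.** Section 3.6.4.2 allocates subjects "in blocks of six consecutive subjects so that two subjects are allocated into each arm", with one of the two TAU subjects assigned to each game for the second 12 weeks. The synopsis (3.1.6) repeats it: "The subjects are randomised into three arms with equal probabilities in blocks of six consecutive subjects". Section 3.6.1 also gives the block length. No varying block size, stratification or concealment step is described; section 3.10.2 says only that groups are handled automatically. Section 3.6.6.3 has all staff trained on the plan.

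**Text under which TAU status is known or can be inferred.** Section 3.6.4.1 confines the blind to the two games: "neither the subjects nor the investigators, CSCs in particular, know whether any given subject is randomised to the MEL-T01 or MEL-S01 study arm". It then says: "Investigators are aware of which subjects are randomised to the TAU arm". Section 3.6.4.3 adds that the CSCs "will have access to the gaming-time and questionnaire-completion-status data of individual identifiable subjects". Under section 3.11.1 TAU subjects have no access to a game before T3.

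**Text under which it is not known.** Section 3.6.4.3 also says: "The CSCs remain blinded to all other investigation data, and especially the data about the study arm". Section 3.10.1 says CSCs see total game time but do not know the group. Section 3.10.2 goes further: "The information regarding the subject group is withheld from all researchers".

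**Discretion before allocation.** Under section 3.6.3.3 and section 3.6.5.2, CSCs confirm eligibility in an interview, and randomisation follows (section 3.10.1). On the suicidality module, "the CSC may use a lower score at their discretion"; section 3.6.5.2 allows the same for the gambling and game-addiction scales.

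**The concern.** Randomisation protects a comparison only if the person deciding on entry cannot foresee the next assignment. Here the block length is constant and written in a document that the screeners know, one arm is open by design, and the screeners have some latitude just before allocation. Anyone who has seen both TAU slots of a block used knows that every remaining slot in it is a game. Anyone who has seen four game slots used knows that only TAU remains. Automatic handling of the list does not prevent this, because the inference comes from counting past allocations, not from seeing the list.

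At stake are the MEL-T01 versus TAU and MEL-S01 versus TAU contrasts, both primary hypotheses (3.5). If borderline subjects were excluded more readily ahead of one kind of slot than the other, the arms would differ before treatment starts.

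**Working it through.** **The plan's own figure.** The documents give no figure for predictability. The only related design figure is the sample size (3.7.4.1: d = 0.40, two-tailed alpha 0.0167, power 0.80). The normal approximation is n = 2(2.393 + 0.842)²/0.40² ≈ 131 per arm. The noncentral t gives 132.2, rounded up to 133, as stated. This point does not affect it.

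**Inputs.** Block of six with 2 TAU and 4 game slots (3.6.4.2); recruitment target 800 (3.7.4.1). Assumption for the ceiling: the start of the block and every earlier TAU/game allocation in it are known at the next screening call.

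**Ceiling.** There are C(6,2) = 15 equally likely TAU/game orders, hence 15 × 6 = 90 slots. A slot is certain when both TAU slots, or all four game slots, have already been used.

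| Position in block | 1 | 2 | 3 | 4 | 5 | 6 | Total |
|---|---|---|---|---|---|---|---|
| Orders (of 15) in which the slot is certain | 0 | 0 | 1 | 3 | 7 | 15 | 26 |

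The certain share is 26/90 = 28.9%, or 0.289 × 800 ≈ 231 subjects. Per block this is 4/3 certain game slots plus 2/5 certain TAU slots, 26/15 = 1.73 of 6. Over all slots, the best guess of TAU versus game is right 74.4% of the time, against 66.7% from always guessing game.

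**Weaker knowledge.** The enumeration was repeated with the latest allocations not yet visible. It was then repeated on the assumption that only positive game time is conclusive, since zero hours may also mean a game subject who has not started. In that case only the certain-TAU slots remain.

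| Latest allocations unseen | All other earlier arms known | Only positive game time conclusive |
|---|---|---|
| 0 | 26/90 = 28.9% | 6/90 = 6.7% |
| 1 | 11/90 = 12.2% | 1/90 = 1.1% |
| 2 | 4/90 = 4.4% | 0 |
| 3 | 1/90 = 1.1% | 0 |

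**Random block sizes.** An observer who knows the menu of sizes and every earlier TAU/game allocation was simulated over 800 subjects, with sizes equally likely. The certain share is about 7% for sizes 6/12 and about 3% for 6/12/18.

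**The case against.** **The plan intends screeners to be blind.** Three sections say that CSCs or all researchers lack the group. The monitoring investigators who receive arm data under 3.6.4.3 see unidentifiable subjects and do not include the CSCs. This stands as a statement of intent, so CSC knowledge of TAU status cannot be treated as settled. It does not dispose of the point. Section 3.6.4.1 says otherwise, and the gaming time the CSCs are given partly reveals the arm. Section 3.10.1 also has them encourage subjects with low play time, which is hard to do without telling game subjects from TAU subjects.

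**The ceiling needs near-immediate knowledge.** The planned dates (1.3.2022 to 31.12.2023, about 96 weeks) imply 800/96 ≈ 8.3 subjects a week, or 800/72 ≈ 11 if the last 24 weeks are follow-up only. A block would then fill in about four to five days, and a lag of three allocations is roughly two days. Game subjects must first install the software and log in, and at least two CSCs share the screening. This stands: a reader might infer that staff foresee 28.9% of allocations, and the documents do not support that.

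**The discretion is limited.** The scales are used only when the CSC is unsure, and the stated latitude is to lower a cut-off, which excludes more people. It does not admit anyone above the cut-off. This stands in the main, although the judgement on suicidal thoughts before any scale is used remains, and selective exclusion is enough to bias a contrast.

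**Analysis can help.** A reader might infer that no analysis could repair such selection. That is too strong. T0 questionnaires are completed before the screening call (3.6.3.3), so selection on measured severity can be examined and adjusted for. Only unmeasured factors are out of reach.

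**Conclusion.** The concern holds as a weakness in allocation concealment combined with a contradiction about who knows TAU status. The share of next allocations that are certain is at most 28.9%, and that requires every earlier TAU/game allocation in the block to be known at screening. More plausible conditions give 12.2%, 4.4% or 1.1% (latest one, two or three unseen), or 6.7% (only positive game time conclusive, no lag). Combining the last condition with a lag of one gives 1.1%.

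These figures measure predictability, not bias. The documents give neither the number of borderline subjects nor any link between discretionary exclusion and PHQ-9 change, so the size of any bias is not quantified. The exposure concerns TAU versus game only. A reader might extend it to MEL-T01 versus MEL-S01, but knowing that a slot is a game slot does not say which game, so that contrast is not directly exposed. The case for change rests on how little the remedy costs, not on evidence that selection has occurred.

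**What to change.** 1. For blocks not yet allocated, have the automated list draw block sizes at random from multiples of six, for example 6, 12 and 18. Multiples of six keep the split of 2 MEL-T01, 2 MEL-S01 and 1 + 1 TAU subjects by later game.
2. Keep the block sizes in a restricted randomisation document and take them out of the plan that CSCs and investigators read.
3. Reconcile sections 3.6.4.1, 3.6.4.3, 3.10.1 and 3.10.2 into one statement of which roles know TAU status, from when, and whether gaming time is visible to whoever screens the next subject.

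The cost is a setting in the allocation program and a wording change. The downside is a slightly larger possible imbalance if recruitment stops mid-block: two arms can differ by at most 2 subjects with blocks of 6 and by at most 6 with a block of 18, small against 133 per arm.

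The change cannot repair past allocations or undo what staff already know. Recruitment status is not stated, and the latest revision (26 February 2024) postdates the planned completion of 31.12.2023. For blocks already allocated, the report can state who knew TAU status, compare T0 scores and screening exclusions between foreseeable and other slots, and adjust the TAU contrasts for T0 measures, noting that this covers measured factors only.
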